## **6.3. Safety Analysis Set**

The safety analysis set includes all enrolled patients who receive at least one dose of study medication.

## **6.4. PK Analysis Set**

### **6.4.1. PK Concentration Set**

The PK concentration population is defined as all treated patients who have at least 1 concentration measured.

### **6.4.2. PK Parameter Set**

The PK parameter analysis population is defined as all enrolled patients treated who have sufficient information to estimate at least 1 of the PK parameters of interest.

CCI

## **6.6. Other Analysis Sets**

### **6.6.1. Modified Intent-to-Treat Set**

The modified intent-to-treat (mITT) is the analysis population that will follow the ITT principle and include subjects receiving at least 1 dose of study medication with baseline assessment and at least 1 post baseline assessment or disease progression or death before the first tumor assessment. The mITT population may be used for interim analysis and conference presentations when the study is still ongoing.

## 6.7. Treatment Misallocations

Subjects who receive the wrong initial dose for whatever reason will be analyzed according to the initial dose actually received. Subjects who receive the wrong dose after the initial dose will be analyzed according to the initial dose received.

## 6.8. Protocol Deviations

All deviations will be listed in the CSR. Major treatment deviations include, but are not limited to, less than 80% of the planned Cycle 1 PF-06647263 dose provided the reduction/omission is not due to treatment-related toxicity. Subjects with major Cycle 1 treatment deviations are not evaluable for MTD.

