**Table 1. Decision Rules**

Number	Number of Patients treated at a Dose level											
	DLT	n=2	n=3	n=4	n=5	n=6	n=7	n=8	n=9	n=10	n=11	n=12
0	E	E	E	E	E	E	E	E	E	E	E	E
1	D	S	S	S	E	E	E	E	E	E	E	E
2	U	D	D	S	S	S	S	S	S	S	S	S
3		U	U	D	D	S	S	S	S	S	S	S
4			U	U	U	D	D	D	D	D	D	S
5				U	U	U	U	U	D	D	D	D
6					U	U	U	U	U	U	U	D
7						U	U	U	U	U	U	U

Cohorts of patients could receive doses already tested but a dose that is associated with decision “Dose de-escalate, unacceptable toxicity” cannot be revisited and no more patients should be treated at this dose or higher doses for the remainder of the trial.

A minimum of 9 patients treated at the MTD dose is required to establish such dose as the RP2D. The maximum sample size would be N=70 but actual sample size will depend on the underlying dose toxicity profile and variability in actual data realization. The initial dosing regimen tested in Part 1 will be PF-06647263 administered once every 3 weeks (Q3W) consistent with the pre-clinical toxicity study. Evaluation of a weekly (QW) regimen will be initiated when the first patient treated with the Q3W regimen experiences a DLT or Grade 2 thrombocytopenia related to study treatment. The starting dose of the QW regimen will not exceed one-third of the highest Q3W dose evaluated. Once initiated, the 2 regimens will be evaluated in parallel and independently based on the same dose-escalation criteria as described above.

Dose escalation will stop under any of the following conditions:

1. The maximum sample size has been achieved;
2. At least 9 patients have been accumulated at a dose that is predicted to be the MTD;
3. All doses explored appear to be overly toxic and the MTD cannot be determined.

### 2.3. Part 2

Upon identification of the MTD, approximately 30 patients will be enrolled at the MTD in order to explore benefit from treatment as suggested by preclinical findings and will better define the safety profile at the RP2D. This expansion component aims at evaluating ADC (PF-06647263) at the MTD in two cancer indications:

- a. Previously treated metastatic TNBC which expresses EFNA-4 (15 patients).
- b. Advanced epithelial ovarian cancer, primary peritoneal or fallopian tube cancer (OVCA) which expresses EFNA-4 and which has progressed or relapsed during or within 6 months post most recent therapy with a platinum agent (15 patients).

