## 7.2. Safety Endpoints

### 7.2.1. DLT Definitions

Severity of adverse events will be graded according to NCI CTCAE version 4.03. For the purpose of dose escalation, any of the following adverse events which are not considered related to disease progression, occurring in the first cycle of treatment (Q3W regimen: 21 days or until the patient receives the 2nd infusion if there are treatment delays, QW regimen: 21 days or until the patient receives the 4th infusion if there are treatment delays) will be classified as DLTs:

- Hematologic:
  - Grade 4 neutropenia lasting >7 days.
  - Febrile neutropenia (defined as neutropenia  $\geq$  Grade 3 and a single body temperature  $>38.3^{\circ}\text{C}$  or a sustained temperature of  $\geq 38^{\circ}\text{C}$  for more than one hour).
  - Grade  $\geq 3$  neutropenia with infection.
  - Any grade thrombocytopenia associated with clinically significant or life-threatening bleeding.
  - Grade 4 thrombocytopenia  $\geq 72$  hours or platelets  $\leq 10,000/\text{mm}^3$  regardless of duration.
- Non-hematologic:
  - Grade  $\geq 3$  toxicities, except those that have not been maximally treated (eg, nausea, vomiting, diarrhea).
  - Delay by more than 2 weeks in receiving the next scheduled cycle due to persisting toxicities attributable to PF-06647263.

Grade  $\geq 3$  cytokine release syndrome, infusion related reaction, allergic reaction, or anaphylaxis will not be considered as DLTs but may be a reason for study discontinuation and should be reviewed with Pfizer.

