### **7.2.2. MTD Definition**

The MTD would be any doses with true toxicity probabilities in the Equivalence Interval (EI) where the EI is defined as [20%-30%].

In practice, the MTD will be the highest dose associated with the occurrence of DLTs  $\leq 33\%$  (eg, 3/9 evaluable patients experience a DLT during the first treatment cycle).

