**Treatment Administration/Compliance**

Listings and tables by dose level will be provided. Cycle length is 21 days. Day 1 of a cycle is the first date of dose within that cycle. The safety analysis set will be used.

Dose modifications may occur in the following ways:

- Cycle delay—Day 1 of current cycle starts later than 21 days from Day 1 of the previous cycle (only applies to cycle 2 and above);
- Dose reduction—A decrease in the administered total daily dose (non-zero) compared to the planned total daily dose upon enrollment. If in the CRF the prescribed dose unit is mg/kg, but the actual dose is in mg the actual dose mg/kg should be calculated considering the body weight of the patient at that visit.

Intra-patient dose escalation is not allowed in this study. The following will be summarized by subject for each dose level:

- Number of subjects per dose level
- Median and range of number of cycles started per subject
- Number (%) of subjects starting a cycle (1, 2, 3...)

- Number (%) of subjects with cycle delays
- Number (%) of dose interruptions (include both known and unknown dates)
- Number (%) of subjects with dose reductions
- Number (%) of each reason (AE vs. Other) for cycle delays, dose interruptions and dose reductions
- Time on treatment (median, range)

The following will be summarized by cycle received for each dose level:

- Total number of cycles started
- Number of cycles started per subject (median, range)
- Number of cycles before 1st delay (median, range)
- Number of cycles before 1st reduction (median, range)
- Number of cycles before 1st interruption (median, range)

The following will be summarized for cumulative dose by dose level and cycle:

- Summary statistics (mean, median, standard deviation and range) of cumulative dose and percent of starting dose (compared to Day 1 dose of each cycle)

Listings by subject (ordered by dose level): start date and stop date of each dosing period within each cycle (including records with 0 mg), administered total daily dose for each period, any missed doses with unknown dates (Y/N), number of missed doses with unknown dates, reason for any dosing changes.

Listings by subject and each cycle (ordered by dose level): cycle length, total planned dose, administered total dose, percentage of planned dose, dose delay (yes/no), dose reduction (yes/no), and dose interruption (yes/no).

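### The SAP's 80%-of-dose test for MTD evaluability checks exposure, not observation, so a Q3W patient lost before the DLT window closes can be counted as DLT-free; the three DLT denominators also disagree

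*SAP*

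**What the plan says.** **Evaluability.** SAP Section 6.8 gives, as an example of a major treatment deviation, "less than 80% of the planned Cycle 1 PF-06647263 dose provided the reduction/omission is not due to treatment-related toxicity". It then adds: "Subjects with major Cycle 1 treatment deviations are not evaluable for MTD". The list is open-ended, and 80% is its only figure.

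**Schedule and window.** Section 2.2 describes the initial regimen as "PF-06647263 administered once every 3 weeks (Q3W"), and Section 9.2.4 says "Cycle length is 21 days". Section 7.2.1 sets the DLT window as "Q3W regimen: 21 days or until the patient receives the 2"nd infusion if treatment is delayed. For QW it is 21 days or until the 4th infusion.

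**Denominators.** There are three:
- Table 1 (Decision Rules, Section 2.2) is indexed by the number of patients treated at a dose level.
- The MTD rule in Section 7.2.2 gives the example "3/9 evaluable patients experience a DLT during the first treatment cycle".
- Section 9.2.1 summarizes Part 1 DLTs on the Per Protocol set. Section 6.2 defines that set under Part 2 only and requires a baseline and a post-baseline disease assessment.

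**The concern.** DLT in Cycle 1 is the Part 1 primary endpoint. A patient without a DLT is informative only if watched for the whole window. The stated test asks how much drug was given and not whether the outcome was seen. Withdrawal or loss to follow-up is not naturally a treatment deviation, so it is doubtful that the open list in Section 6.8 reaches it.

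Cohorts have 2 to 4 patients, so one unobserved patient can settle a dose decision. A U decision also closes that dose and all higher doses for the rest of the trial, so whether a cell reads D or U has lasting effect.

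The same patient may be in the Table 1 count, arguably outside the MTD count, and in or out of the final DLT summary for a reason unrelated to toxicity, namely whether a tumor assessment was done.

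**Working it through.** **1. What the 80% test can detect.** Share = infusions received / infusions planned in Cycle 1, assuming equal and complete infusions. Three QW infusions per cycle is inferred from the 4th-infusion limit in Section 7.2.1.

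| Regimen | Last infusion before leaving | Share | Flagged (<80%)? |
|---|---|---|---|
| Q3W | 1st | 1/1 = 100% | No |
| QW | 1st | 1/3 = 33% | Yes |
| QW | 2nd | 2/3 = 67% | Yes |
| QW | 3rd | 3/3 = 100% | No |

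After a complete Q3W infusion the test cannot flag anyone. On QW it catches most early leavers, unless the omission was due to treatment-related toxicity.

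**2. Reproducing Table 1.** Unit probability mass = posterior probability of an interval / its length. The intervals are 0–0.20, 0.20–0.30 and 0.30–1, and U applies if Pr(p > 0.25 | data) > 0.975 (Section 4.2.1). The prior is not stated; Beta(1,1) is assumed.

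Example for 2 DLTs:
- 2/5, posterior Beta(3,4), CDF 0.0989 at 0.20 and 0.2557 at 0.30: E = 0.0989/0.20 = 0.49, S = 0.1568/0.10 = 1.57, D = 0.7443/0.70 = 1.06. Decision S, as printed.
- 2/4, posterior Beta(3,3), CDF 0.0579 and 0.1631: E = 0.29, S = 0.1052/0.10 = 1.05, D = 0.8369/0.70 = 1.20. Decision D, as printed.

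Up to n = 12, 68 of 73 printed cells are reproduced. This includes 1/2, where S and D tie exactly (0.112/0.10 = 0.784/0.70 = 1.12) and the SAP prints D. The cells that differ are 1/6, 4/10, 4/11, 4/12 and 5/12. The extracted table has 12 entries per row under 11 column heads, so these differences are not called errors.

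**3. Effect of one unobserved patient on the printed table.** Each x/n cell for n = 3 to 12 was compared with x/(n−1): 65 comparisons, 8 changes.

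| Counted as DLT-free | Excluded |
|---|---|
| 1/6: E | 1/5: S |
| 1/3: S | 1/2: D |
| 2/5: S | 2/4: D |
| 3/7: S | 3/6: D |
| 2/3: D | 2/2: U |
| 3/5: D | 3/4: U |
| 4/7: D | 4/6: U |
| 5/10: D | 5/9: U |

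Counting the patient gives the less cautious decision in all 8. Seven also appear in the recomputed table (the 1/3 change relies on the tie at 1/2). The 1/6 change does not, because the recomputation gives S at both 1/6 and 1/5.

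**4. Effect on the rate, if such patients are counted as DLT-free.** Apparent rate = p × [1 − L(1 − f)], where L is the share lost early and f is the fraction of their DLT risk that was observed. The SAP gives neither; L = 5% to 30% is assumed.

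| True p | f = 0 | f = 0.5 |
|---|---|---|
| 25% | 23.75% to 17.5% | 24.4% to 21.25% |
| 30% | 28.5% to 21.0% | 29.25% to 25.5% |

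At an assumed true rate of 35%, the binomial P(at most 3 DLTs) is 0.61 with 9 patients fully observed. It is 0.71 with 8 observed and 1 unobserved patient counted as DLT-free.

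**5. Direction in the final summary.** Take a hypothetical dose with 9 treated and 3 DLTs (33.3%), where one patient has no post-baseline disease assessment. If that patient had a DLT, the Per Protocol figure is 2/8 = 25.0%. If not, it is 3/8 = 37.5%. The bias can go either way.

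**The case against.** The strongest reply is that the SAP supplements a protocol not shown here, and that evaluability and replacement rules often sit there. That would answer a complaint about missing detail. It does not fully answer this one, because Section 6.8 itself sets an evaluability rule, and the rule works badly for Q3W.

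Several stronger readings are tempting but not supported:

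- **That the SAP counts unobserved patients as DLT-free.** It nowhere says so. The deviation list is open, Section 7.2.2 speaks of evaluable patients, and Section 4.2.1 places allocation after the Cycle 1 safety assessment is complete. The text permits such counting; it does not direct it.
- **That every early leaver is affected.** Stopping treatment does not stop safety observation. Section 2.1 plans a follow-up visit within 4 weeks of the last dose, and Section 7.2.6 counts non-fatal AEs to 28 days after the final dose or to new anti-cancer treatment. After one Q3W infusion, 28 days outlasts the 21-day window. Only patients truly lost, refusing follow-up or starting new therapy early are at issue. Section 6.2 does list unpermitted anticancer treatment as a major deviation, but under Part 2.
- **That the design is pushed to escalate.** Only the 1/6 cell concerns escalation, and it is not reproduced. Four changes are D instead of U, where the dose is reduced either way and only the bar on returning differs.
- **That the SAP's 3/9 example fails as 3/8.** Those nine are described as evaluable, so an unobserved patient cannot be assumed among them. Eight would also miss the minimum of 9.
- **That the test fully protects QW.** A patient lost after the third infusion passes it too.

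**Conclusion.** The point holds in limited form. The stated test cannot identify a Q3W patient whose DLT window was not observed, and no SAP section requires that observation. The treated, evaluable and Per Protocol denominators are not reconciled, and the Per Protocol set named for Part 1 has no Part 1 definition.

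One such patient counted as DLT-free alters 8 of 65 printed decisions, all in the less cautious direction: four D for U, three S for D, and one E for S that is not reproduced under the assumed Beta(1,1) prior. The other 57 are unchanged.

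The effect on the trial depends on an early-loss rate that the SAP does not give, so the dilution figures are conditional. No net direction can be claimed for the final DLT summary. This should be corrected in the SAP; it is not evidence that any dose decision was or will be wrong.

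**What to change.** Define one DLT-evaluable set for Part 1 in Section 6: treated patients who either
- had a DLT in Cycle 1, or
- received at least the SAP's own 80% of the planned Cycle 1 dose and were observed for safety to the end of the Section 7.2.1 window for their regimen.

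Use this set for the Table 1 counts, the MTD rule in Section 7.2.2 and the DLT summary in Section 9.2.1, where it replaces the Per Protocol set. Say how Section 6.8's allowance for toxicity-related reductions applies to it. Reconcile the set with any evaluability or replacement rule in the protocol. List treated patients left out of the set, with the reason and last day observed.

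The cost is SAP wording plus an occasional replacement patient before a cohort decision. No dose, schedule or DLT criterion changes.

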## **6.2. 'PER PROTOCOL' Analysis Set**

Part 2: the per protocol (PP) analysis sets includes all enrolled patients (for each indication) who receive at least one dose of study medication and who do not have major treatment deviations during first cycle.

Specifically: Patients with major treatment deviations in Cycle 1 are not evaluable for the RP2D assessment and therefore will not be included in the PP analysis. Major deviations include failure to satisfy major entry criteria (eg, confirmation of the target disease; signed informed consent) or use of other anticancer treatments during the active treatment and disease follow-up phases other than as defined/allowed in this protocol. At least one baseline and one post-baseline disease assessment are required for the PP analysis.

Modified PP analysis sets may be considered for additional analyses and would include patients enrolled either in Part 1 or in Part 2.

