# 7. ENDPOINTS AND COVARIATES

## 7.1. Efficacy Endpoint(s)

Objective tumor response, as assessed using the Response Evaluation Criteria in Solid Tumor (RECIST) version 1.1 by calculating the Overall Response Rate (ORR), Progression Free Survival (PFS), and Overall Survival (OS).

All efficacy endpoints are secondary in this study, which include objective tumor response, progression-free survival (PFS), and overall survival (OS) for each tumor type in the expansion cohorts. The above efficacy endpoints are derived based on the disease response per investigator evaluation on the CRF pages, which is the primary method of documentation of disease.

- **Overall Response (OR)** – or Response Rate (RR) is defined as complete response (CR) or partial response (PR) according to RECIST 1.1 ([Appendix 2](#)). Overall response is the best response recorded from first dose until disease progression/recurrence.
- **Progression Free Survival (PFS)** - is defined as the time from Cycle 1 Day 1 (C1D1) to first documentation of disease progression or to death due to any cause, whichever occurs first. Subjects last known to be 1) alive 2) on treatment or within the post-treatment follow-up period and 3) progression-free, are censored at the date of the last disease assessment that verified lack of disease progression. Subjects who start new anti-cancer treatment prior to the end of post-treatment follow-up period and have adequate baseline and on-treatment objective disease assessments without evidence of progressive disease are censored at the date of the last objective disease assessment. Subjects with inadequate baseline or no on-study disease assessments are censored at C1D1 unless death occurred prior to the first planned assessment (in which case the death is an event). Subjects with at least one on-study disease assessment who discontinue treatment without disease progression and without death within 28 days of discontinuation are censored at the date of the last objective disease assessment that verified lack of disease progression (if progression or death is within 28 days of discontinuation the progression or death is an event). Subjects with documentation of progression or death after an unacceptably long interval (>16 weeks) since the previous disease assessment will be censored at the time of the previous assessment.

PFS (days) = [progression/death date – C1D1 + 1].

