#### **9.2.2. Secondary Analyses**

##### **9.2.2.1. Efficacy Analysis**

In this Phase 1 study efficacy is a secondary objective. Note that the efficacy analysis is to be conducted by malignancy for patients in the MTD expansion cohorts who are in the Safety Analysis Set and have baseline disease assessment and at least one post-baseline disease assessment. In the event that a large number of patients in the escalation portion of the study have the same malignancy, the efficacy analysis may be conducted.

Summary tables of best Overall Response Rate, Progression Free Survival, and Overall Survival will be provided overall and by malignancy. Efficacy listings will be provided that include best response, first CR/PR date, last date with CR or PR, most recent date without progression, progression date, death date, date of first response and last tumor assessment date, etc.

A response rate overall for Part 1 dose escalation and response rates by low, medium, and high dose groups may be presented.

The following table provides an overview of the efficacy analysis.

Endpoint	Analysis Set	Statistical Method	Model/ Covariates/ Strata	Missing Data	Interpretation
Overall response	Per Protocol, expansion cohorts, etc.	Exact CI	By dose range/ malignancy	Censored per Section 11.3	Secondary Analysis
Progression Free Survival (PFS)	Per Protocol, expansion cohorts	Kaplan-Meier	By malignancy	Censored per Section 11.3	Secondary Analysis
Time to Progression (TTP)	Per Protocol, expansion cohorts	Kaplan-Meier	By malignancy	Censored per Section 11.3	Secondary Analysis
Duration of Response (DR)	Per Protocol, expansion cohorts	Kaplan-Meier	By malignancy	Censored per Section 11.3	Secondary Analysis

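### Section 6.8 exempts only treatment-related toxicity from its 80% Cycle 1 dose rule, so on the weekly regimen a DLT not attributed to the drug can remove its own patient from the MTD assessment

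*SAP*

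**What the plan says.** Section 6.8 (Protocol Deviations) lists among major treatment deviations "less than 80% of the planned Cycle 1 PF-06647263 dose provided the reduction/omission is not due to treatment-related toxicity". It then states the consequence: "Subjects with major Cycle 1 treatment deviations are not evaluable for MTD".

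Section 7.2.1 (DLT Definitions) counts as DLTs "any of the following adverse events which are not considered related to disease progression" when they occur in the first cycle. Within its list, only the criterion for a delay of more than two weeks requires attribution to the study drug. The weekly window is "QW regimen: 21 days or until the patient receives the" fourth infusion if there are delays, and section 9.2.4 adds "Cycle length is 21 days".

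Section 6.2 restricts the Per Protocol (PP) set to treated patients "who do not have major treatment deviations during first cycle" and also requires a baseline and a post-baseline disease assessment. It carries a Part 2 label, but section 9.2.1 uses the PP set for the Part 1 DLT summary, which is the primary analysis.

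For efficacy, the overview table in section 9.2.2.1 assigns "Per Protocol, expansion cohorts" to PFS, time to progression and duration of response, and a similar PP entry to overall response. The narrative of the same section instead uses Safety Analysis Set patients with baseline and post-baseline assessments and sets no dose condition.

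**The concern.** The exemption in 6.8 is narrower than the DLT definition in 7.2.1. An event judged unrelated both to progression and to the drug is a DLT under 7.2.1. If it also stops dosing, the shortfall is not due to treatment-related toxicity, so 6.8 makes the patient not evaluable. No sentence in the SAP keeps a patient with a DLT evaluable after a short Cycle 1 dose.

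The exclusion is then caused by the outcome being measured. A DLT that 7.2.1 says must count would disappear from the Part 1 primary endpoint and from the MTD assessment. Part 1 enrols cohorts of 2 to 4, so a single lost DLT can change what happens at a dose level.

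**Working it through.** **Step 1: can the rule be triggered?** Planned Cycle 1 infusions on QW: a 21-day cycle with weekly dosing and a DLT window closing at the fourth infusion gives three.

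- One infusion given: 1/3 = 33.3%, below 80%.
- Two given: 2/3 = 66.7%, below 80%.

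One permanently omitted infusion is enough. On Q3W, Cycle 1 is a single infusion, and an event after a full infusion leaves 100%. The problem is therefore essentially confined to QW.

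**Step 2: the two tests side by side**, for a QW patient with a qualifying event that stops dosing before the third infusion.

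| Event judged | DLT under 7.2.1? | Evaluable under 6.8? |
|---|---|---|
| Drug-related | Yes | Yes, exempt |
| Progression-related | No | No |
| Neither | Yes | No |

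The last row is the contradiction.

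**Step 3: reproduce the plan's decisions.** Inputs from sections 2.2 and 4.2.1: target 0.25, interval 0.20 to 0.30, exclusion cutoff 0.975. The SAP names no prior, so Beta(1,1) is assumed. With x DLTs in n patients the posterior is Beta(1+x, 1+n−x), and the unit probability masses are:

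- under = Pr(p<0.20)/0.20
- proper = Pr(0.20<p<0.30)/0.10
- over = Pr(p>0.30)/0.70

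The largest gives E, S or D respectively. U applies if Pr(p>0.25)>0.975. Every printed Table 1 cell at n = 2 to 5 is reproduced.

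**Step 4: remove one DLT patient**, x/n to (x−1)/(n−1). Masses are shown as under / proper / over.

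| DLT counted | DLT patient removed |
|---|---|
| 1/3: 0.904 / 1.675 / 0.931, S | 0/2: 2.440 / 1.690 / 0.490, E |
| 1/4: 1.314 / 2.091 / 0.755, S | 0/3: 2.952 / 1.695 / 0.343, E |
| 2/4: 0.290 / 1.052 / 1.196, D | 1/3: 0.904 / 1.675 / 0.931, S |
| 3/4: Pr(p>0.25) = 0.984, U | 2/3: 0.136 / 0.565 / 1.309, Pr(p>0.25) = 0.949, D |

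All eight entries agree with the printed table. In the last row the bar that section 2.2 places on a U dose and all higher doses is no longer triggered.

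**Step 5: direction over the whole table.** There are 60 pairs with at least one DLT at n = 3 to 12. In the printed table 22 change; in the direct computation 20 change. Every change in both is towards less caution. These are counts of cells, not probabilities: 38 of 60 printed pairs (60 − 22) do not change, and some cells will rarely arise.

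**The case against.** **The scenario is narrow.** It needs the QW regimen, which opens only once a Q3W patient has a DLT or related Grade 2 thrombocytopenia. It also needs an event attributed neither to progression nor to the drug, and an infusion that is omitted for good. A delay alone is not enough, because the QW window stretches to the fourth infusion and late infusions can complete the cycle dose. The SAP gives no frequency for such events. This stands, and it limits how often the problem can occur.

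**The link to Table 1 is inferred.** Table 1 is headed by patients treated, while 6.8 speaks of evaluability for MTD. A team could keep such a patient in the Table 1 count and still leave the patient out of the MTD assessment. This also stands. The exclusion from the MTD assessment is stated outright. The effect on escalation decisions is conditional.

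**Stronger readings the document does not support:**

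- A reader might infer that early progression removes a patient from the DLT count. A DLT-free progressor contributes no DLT and leaves only the denominator. That raises the observed rate, and treating such a patient as not evaluable is not in itself an error.
- A reader might infer that 6.8 defeats the section 7.1 rule that a patient without assessments is censored "unless death occurred prior to the first planned assessment (in which case the death is an event". A patient who dies unscanned leaves the PP set through the post-baseline assessment requirement in 6.2, whatever dose was given. Amending 6.8 would not bring that patient back.
- A reader might infer that early failures drop out of efficacy generally. The 9.2.2.1 narrative keeps scanned progressors, OS is measured in the intent-to-treat population, and the SAP does not say that Part 2 will use QW.
- A reader might take 4/10 D to 3/9 S from the printed table as a further example. Computed directly, 4/10 gives 0.252 / 1.599 / 1.128, which is already S, so nothing changes. The rows of Table 1 as available hold 12 entries under 11 headed columns, so larger-n cells should not carry the argument.

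**Conclusion.** The mismatch between 6.8 and 7.2.1 is real and bears on the Part 1 primary endpoint. On QW, a DLT attributed neither to progression nor to the drug that permanently halts Cycle 1 dosing makes the patient not evaluable for MTD. The patient also leaves the PP DLT summary, taking the 6.2 definition to apply to Part 1 as section 9.2.1 implies.

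The case should be infrequent, but where a decision changes it changes in one direction only. If these patients also leave the Table 1 counts, one lost DLT can turn S into E (1/3, 1/4), D into S (2/4) or U into D (3/4). Those four examples hold in the printed table and under the assumed Beta(1,1) prior. Q3W is largely unaffected.

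A secondary and narrower point remains for efficacy. Under the PP entry in the 9.2.2.1 table, but not under that section's narrative, a QW expansion patient with scan-documented Cycle 1 progression and less than 80% of the dose would be dropped from response, PFS, time to progression and duration of response. This applies only if Part 2 uses QW, and the SAP gives no basis for putting a size on it.

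**What to change.** Reconcile 6.8 with 7.2.1. State in 6.8 that the 80% test applies only to patients without a DLT, so that any patient with a DLT under 7.2.1 is evaluable for MTD and included in the DLT summary whatever share of the Cycle 1 dose was received. State in the same place whether the Table 1 counts use treated or evaluable patients.

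For the secondary point, add to 6.2 that a Cycle 1 shortfall caused by documented progression is not a major treatment deviation for the efficacy set.

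The cost is a few sentences of SAP wording and no new data. The downside is that an occasional DLT at reduced exposure will count against the dose. The efficacy sentence would keep some early progressors in the PP estimates, making them slightly less favourable.
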